4.2 SCIENTIFIC RATIONALE FOR STUDY DESIGN

The investigators would like to address limitations in the studies done by Moo and Shin by conducting a prospective, randomized trial.

This study is designed to assess if applying bone wax to exposed cancellous bone during total knee arthroplasty provides superior hemostasis. Patients will be randomized to receive bone wax (treatment group) or no bone wax (control group). Blood loss will be calculated using the Hb-balance Formula to provide a consistent measurement of perioperative and postoperative bleeding. All other standard of care intraoperative blood minimizing strategies will be consistent for these patients. These strategies include pneumatic tourniquet, intravenous tranexamic acid, and spinal anesthesia. The Inclusion/Exclusion criteria were developed to ensure this consistency.

Objective and functional outcomes will be obtained using the 2011 Knee Society Score (KSS). The KSS will be completed preoperatively and postoperatively at the 8 week visit, or the visit closest to this time point., (Appendix B- Preoperative/Postoperative 2011 Knee Society Scores)

Preoperatively patients taking anticoagulants or antiplatelets, with the exception of aspirin 81 mg daily, will be excluded from the study as these medications could adversely affect intraoperative and postoperative bleeding. Patients with any bleeding dyscrasias will also be excluded from the study. Patients who are unable to stop these products for any reason will be excluded from the study.

Laboratory testing done as standard of care for all preoperative surgical patients are comprehensive metabolic panels and complete blood count. These laboratory values will be used to evaluate the inclusion and exclusion criteria for study enrollment. This study does not require any study specific laboratory tests.

On the operative day patients will be interviewed to confirm their agreement to continue in the study. Patients will be re-consented by [name] or [name] if the date of the original consent is greater than 30 days from the date of surgery. The inclusion and exclusion criteria will be verified prior to study randomization using the laboratory testing done in Pre-surgical Testing (PST) and the preoperative medical history documents. Patients will be randomized to either the treatment group (bone wax) or the control arm (no bone wax). The operating room (OR) staff will be notified of the treatment arm.

Intraoperative blood management strategies will be consistent for all subjects to avoid any confounding factors which could affect postoperative transfusion requirements. Any patients unable to be treated according to the department treatment guidelines will be excluded from the study. Intraoperatively blood loss is minimized by anesthetic techniques, pharmacologic interventions, and surgical techniques, as per standard of care and department treatment guidelines.

The patient and the postoperative hospital staff will be blinded to the treatment arm. The OR staff will be trained not to discuss this information with the patient. During the transition of care from the OR to the Post Anesthetic Care Unit (PACU) the use of bone wax is not routinely included in the verbal patient report. The lack of this information is not required to effectively manage the patient in the postoperative period and will not affect patient care. Postoperatively medical care is managed by the hospitalist, medical doctors specializing in the care of hospitalized patients. Hgb and Hct are drawn daily during the patient's hospitalization as per the standard of care. These values will be used to calculate the Hb-balance Formula.

Blood loss will be calculated using the Hb-balance Formula. This method is being used to provide a more standardized method of calculating blood loss. Eipe and Ponniah showed that surgical blood loss was underestimated by 64% when clinical methods are used to assess blood-soaked sponges and blood lost to suction bottles and the vacuum drain.⁷

Following discharge patients will be followed in the outpatient surgical office according to the postoperative standard of care visit schedule. Results of the 2011 KSS Objective and Functional Outcome Measurements administered as part of standard of care at the 8 week postoperative visit, or the office visit closest to these time points will be collected for research purposes. Patients will be called at 56 days (+2weeks) from the date of surgery for any device related adverse events. This call is standard of care for the department. Three attempts will be made to reach the patient before they are considered "lost to follow-up".

4.3 JUSTIFICATION FOR DOSE

Not Applicable

4.4 END OF STUDY DEFINITION

A participant is considered to have completed the study if he or she has completed all phases of the study including the last visit or the last scheduled procedure shown in the Schedule of Activities (SoA), Section 1.3.

5 STUDY POPULATION

5.1 INCLUSION CRITERIA

Inclusion criteria:

1. Patients scheduled for primary unilateral total knee arthroplasty
2. Preoperative Hemoglobin $\geq 11\text{mg/dL}$
3. Preoperative platelet count of $\geq 150,000$
4. Age >18
5. Patient is freely able to provide consent
6. Patient willing to complete all study related procedures

5.2 EXCLUSION CRITERIA

1. Patients unable to take aspirin or apixaban for VTE prophylaxis
2. Allergy to any of the ingredients in bone wax (beeswax, paraffin, or isopropyl palmitate)
3. Patients taking clopidogrel (Plavix), ticagrelor (Brilinta), or prasugrel (Effient) or any other antiplatelet medication (except for aspirin 81 mg)
4. Patients unable to get IV TXA for any reason
5. Patients requiring anticoagulant treatment prior to surgery
6. Any medical condition that in the opinion of the investigator would require special fluid management protocols during or after surgery
7. Allergy to TXA

8. Blood transfusion within 1 month of surgery
9. Patients who are unwilling to undergo blood transfusion, if necessary
10. Patients who have habitual opioid use
11. Patients who have a psychiatric or mental illness which could impair the consent process or ability to complete patient-reported questionnaires
12. Fixed motor deficit affecting functional assessment of the knee
13. Patients with a contraindication to spinal anesthesia
14. Patients receiving erythropoietin therapy for anemia
15. Patients who are unable to stop their daily aspirin, aspirin-like products, and/or non-steroidal anti-inflammatory agents 7 days prior to surgery for any reason
16. Patients with a contraindication for the pneumatic tourniquet applied in the operating room

5.3 LIFESTYLE CONSIDERATIONS

There are no lifestyle modifications or requirements for this study.

5.4 SCREEN FAILURES

Screen failures are defined as participants who consent to participate in the clinical trial but are not subsequently randomly assigned to the study intervention. A minimal set of screen failure information is required to ensure transparent reporting of screen failure participants, to meet the Consolidated Standards of Reporting Trials (CONSORT) publishing requirements and to respond to queries from regulatory authorities. Minimal information includes demography, screen failure details, and eligibility criteria.

5.5 STRATEGIES FOR RECRUITMENT AND RETENTION

Participation in the clinical trial will be discussed with the patient by [name], [name], or a designee, when the patient is first scheduled for a unilateral total knee arthroplasty. The investigator will discuss the following:

- the purpose/objective of the study
- the study design (e.g., the number of participants)
- how patients are assigned to the treatment group

- participation in this study is not required
- patients may withdraw from this study at their discretion

Consent will be obtained at any time during the preoperative period. The patients will be provided with contact information for the research staff for any questions or concerns.

This study will not be including any vulnerable or cognitively impaired patients.

6 STUDY INTERVENTION

6.1 STUDY INTERVENTION(S) ADMINISTRATION

6.1.1 STUDY INTERVENTION DESCRIPTION

Bone Wax is commercially available and is being used in accordance with approved labeling. During total joint arthroplasties bone wax is softened and applied firmly on the exposed cancellous bone around the prostheses by the orthopaedic surgeon after implant cementing. . (Appendix C-Bone Wax Package Insert)

6.1.2 DOSING AND ADMINISTRATION

Bone wax should be used immediately after removal from the package. Softened Bone Wax is applied to the bone edges as indicated by the surgical circumstances and the preference of the surgeon. Exposed cancellous bone surface can vary between patients. In order to capture this variance the surgeons will calculate the amount of exposed bone by the following method:

Once the distal femoral cut and prep for the chamfer cuts and notch cut is complete:

1. Measure the distal femur medial to lateral (ML) distance.
2. Measure the distance from anterior chamfer to most proximal portion of exposed anterior femoral bone.
3. Measure the ML distance of anterior chamfer.
4. Measure the height of the notch cut, meaning, the anterior posterior (AP) distance (notch surface).

Those measurements will be collected as well as the femoral implant size.

Calculations of surface area:

1. ML surface - will be calculated as ML distance - ML width of the implant. That number, will be than be multiplied by the combined length of the implant distal condyl and anterior chamfer.
2. Anterior surface - which is mostly a triangle shaped will be calculated as, ML distance of anterior chamfer (triangle base) times the triangle height which is distance from anterior chamfer edge to most proximal exposed bone on the anterior cut divided by 2. From that surface area, the implant anterior flange area will be deducted.
3. Notch surface - will be calculated as AP notch height X width of the notch. For implant size 2-5 there is the same notch width, and 6-10 have same notch width.

Combining the value of 1+2+3, is the overall exposed bone surface that needs bone wax coverage.

The exposed bone surface will be document by following grading system:

Grade 1: up to 3 millimeters (mm) of exposed bone

Grade 2: >3 to 6 mm exposed bone

Grade 3: >6 mm exposed bone

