1.3 SCHEDULE OF ACTIVITIES (SOA)

VISIT WINDOW	PREOPERTIVE PERIOD	DAY OF SURGERY	HOSPITALIZATION	8 WEEK PO VISIT (SOC)	2 MONTH FOLLOW-UP PHONE CALL (SOC)
CONSENT	X				
DEMOGRAPHICS	X				
PRESURGICAL TESTING HISTORY & PHYSICAL (SOC)	X				
PREOPERATIVE KNEE SOCIETY SCORE	X				
CONFIRM INCLUSION/EXCLUSION	X				
RANDOMIZATION		X			
SURGEON TO GRADE AMOUNT OF EXPOSED BONE		X			
DAILY HGB/HCT (SOC)			X		
POSTOPERATIVE KNEE SOCIETY SCORE				X	
DEVICE ADVERSE EVENTS		X	X	X	X

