The limitations in the Moo et al. study were, they did not collect postoperative outcomes such as pain, range of motion, and Knee Society Score (KSS). Efficacy and safety data are lacking in this publication as most patients were transferred to a rehabilitation facility. Long term follow-up on clinical outcomes such as range of motion and functional assessment scores were not reported. The study subjects consisted of patients with osteoarthritis of the knee only, thereby, excluding whether patients with other inflammatory arthritis may benefit from the use of bone wax. The use of a chemical hemostatic agent tranexamic acid (TXA) was also excluded from the surgical procedure. The incorporation of TXA could have increased the level of hemostasis.

A recently published manuscript by Shin, et al also evaluated blood loss outcomes with the use of bone wax. Though this study also found bone wax reduced blood loss there were several limitations to the study. First, its retrospective design is inherently disadvantageous. Second, the postoperative outcomes such as pain score, range of motion, length of stay and clinical scores, were not compared between the groups. Third, although there was no significant intergroup difference in the radiologic prosthetic coverage of the osteotomy surface, the area of the cancellous bone surface uncovered by the femoral and tibial components were not evaluated intraoperatively. The area of residual osteotomy might be associated with the volume of blood loss and consequently with transfusion rates because osseous hemorrhage is one of the main bleeding sources.⁵

The investigators would like to address limitations in these studies by conducting a prospective, randomized trial. This study will also be collecting outcome measures (Knee Society Score) which were noted limitations of these studies. Additionally, the surgeons will be measuring the amount of exposed cancellous bone in the OR. The method to be used is referenced in this protocol.

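### Does grading exposed bone in millimetres, when section 6.1.2 calculates it as an area, call for a change to the plan?

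*Combined protocol and SAP*

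**What the plan says.** Section 6.1.2 (Dosing and Administration) recognises that exposed cancellous bone differs between patients and sets out how to record it. The surgeon takes four femoral distances: the medial-lateral (ML) width of the distal femur, the height of the exposed anterior bone, the ML width of the anterior chamfer, and the anterior-posterior height of the notch cut. On data capture it says "Those measurements will be collected as well as the femoral implant size".

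Three areas are then calculated. The last is typical: "Notch surface - will be calculated as AP notch height X width of the notch". They are added: "Combining the value of 1+2+3, is the overall exposed bone surface that needs bone wax coverage". The text goes straight on to "The exposed bone surface will be document by following grading system", and the scale opens with "Grade 1: up to 3 millimeters (mm) of exposed bone". Grade 2 runs from above 3 to 6 mm and Grade 3 is anything above 6 mm.

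Two other places mention the item. The Schedule of Activities (1.3) lists "SURGEON TO GRADE AMOUNT OF EXPOSED BONE" on the day of surgery. The Background (2.2) notes of an earlier retrospective study that "the area of the cancellous bone surface uncovered by the femoral and tibial components were not evaluated intraoperatively", and says of the present trial's measurement: "The method to be used is referenced in this protocol". Neither place adds a unit or a definition.

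**The concern.** The same term, exposed bone surface, is calculated as length squared and then graded as a length. If the grade is meant to be an area, the unit is wrong or the cut-points are. If it is meant to be a length, there are at least five candidates (the four measured distances and the ML difference between bone and implant), and none is named.

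This does not look like a fault of text extraction, since Grade 1 spells the unit out in words. Two surgeons operate in this trial, and each could read the scale differently, so the same knee could receive different grades. The protocol also offers intraoperative measurement of exposed bone as an improvement on earlier work. If the grade carried that aim, or entered an analysis as a covariate, stratum or subgroup, its meaning would depend on the reader's choice of unit.

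**Working it through.** **Step 1: dimensions.** Inputs are the formulas in section 6.1.2. The section gives no unit for the measured lengths; take millimetres.

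- ML surface: (ML distance − implant ML width) × implant length = (mm − mm) × mm = mm².
- Anterior surface: base × height / 2 − flange area = mm × mm / 2 − mm² = mm².
- Notch surface: height × width = mm × mm = mm².
- Sum: mm². Cut-points: 3 mm and 6 mm.

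The mismatch is confirmed. There is no printed total or worked example in the plan to reproduce.

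**Step 2: could mm simply mean mm²?** The cut-points would be the areas of squares of side √3 = 1.73 mm and √6 = 2.45 mm. The documents give no bone or implant dimensions, so the following are assumptions. A notch of 5–30 mm by 5–20 mm has an area of 5 × 5 = 25 to 30 × 20 = 600 mm². An ML difference of 0.5–6 mm along 20–60 mm gives 0.5 × 20 = 10 to 6 × 60 = 360 mm². Either component alone exceeds 6 mm² across its whole range. Provided the remaining components are not negative (two of the formulas contain subtractions), nearly every knee would be Grade 3 and the scale would not discriminate.

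**Step 3: do the readings differ?** They can. Take an assumed knee with a 15 × 15 mm notch, an ML difference of 2 mm along 40 mm, and a net anterior area of 50 mm²:

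2 × 40 + 50 + 15 × 15 = 80 + 50 + 225 = 355 mm² = 3.55 cm².

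| Reading | Value | Grade |
|---|---|---|
| mm² | 355 (> 6) | 3 |
| cm² (a unit the protocol never uses) | 3.55 (> 3, ≤ 6) | 2 |
| ML difference in mm | 2 (≤ 3) | 1 |

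This shows that disagreement is possible. How often it would occur cannot be estimated from the documents.

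**Step 4: where does the grade go?**

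| Possible use | Section | Grade used? |
|---|---|---|
| Endpoint | 1.1, 3 | No |
| Stratified randomization | 4.1 | No; no stratification |
| Guide to wax application | 6.1.2 | No; left to the operative situation and the surgeon's preference |
| Sample size | 9.2 | No; rests on blood loss and its standard deviation |
| Primary analysis | 9.4.2 | No; unadjusted two-sample t-test |
| Secondary analyses | 9.4.3 | No; mixed models for hemoglobin, hematocrit and KSS |
| Subgroup or exploratory analysis | 9.4.7, 9.4.9 | None planned |

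**Step 5: what is kept?** The area depends on the four lengths and on implant dimensions (ML width, condyle plus chamfer length, flange area, notch width). The lengths and the implant size are recorded. If those dimensions are fixed by implant size, as 6.1.2 indicates for notch width within size ranges, the continuous area can be derived without using the grade.

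**The case for a change.** The best case for a change is that the undefined item is the scheduled procedure itself: section 1.3 asks the surgeon to grade, not to compute an area. Section 2.2 points to this protocol for the method, two surgeons will apply the scale, and clearer wording would be cheap. A three-level grade whose level depends on the unit chosen cannot sensibly be published.

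Much of that stands. The wording is inconsistent, and the grade should not be reported as it is. But the stated aim is to capture how much bone is exposed, and the stored lengths and implant size serve it better than three categories would. A manual of procedures is mentioned in 10.1.10 and may define the grade; it was not available, so nothing here relies on it.

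A second argument is that section 9.4.1 promises baseline descriptives and formal tests on all other outcomes, without saying whether the grade is among them. It is not listed as an outcome in section 3. If exposed bone does appear in a descriptive table, an analyst can show the derived area, and the treatment comparisons are untouched.

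A third is that the earlier study's gap concerned femoral and tibial components, whereas this measure is femoral. The formula is explicit: all three components are femoral, so tibial bone is outside it. That is a choice of scope and separate from the unit question.

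One limit should be conceded. If the investigators intended some distance that is not recorded, such as a maximum rim width, the grade could not be rebuilt from the stored data. The area still could.

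**Conclusion.** The area-versus-length inconsistency in section 6.1.2 is genuine, but correcting it would bring no gain to any planned result. No endpoint, allocation, sample size or analysis in the plan uses the grade, so the change in every planned estimate, test and conclusion is zero whichever reading the surgeons adopt. Following the plan as written leaves the primary t-test and the secondary mixed models sound.

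The loss is confined to one descriptive three-level variable, and a finer replacement is available from data already collected. This rests on two assumptions: that the four lengths and implant size are recorded as 6.1.2 states, and that the implant's dimensions by size can be obtained, since the documents do not print them. The conclusion would differ only if the grade were later used as a covariate or subgroup variable, which the plan does not propose.

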6.2 PREPARATION/HANDLING/STORAGE/ACCOUNTABILITY

6.2.1 ACQUISITION AND ACCOUNTABILITY

Not Applicable

6.2.2 FORMULATION, APPEARANCE, PACKAGING, AND LABELING

Bone wax is a sterile mixture of beeswax, paraffin, and isopropyl palmitate. It is opaque and has a waxy odor. Bone wax is available sterile in individual foil envelopes.

6.2.3 PRODUCT STORAGE AND STABILITY

No special storage conditions are required.

6.2.4 PREPARATION

Using aseptic technique, Bone wax should be warmed to desired consistency by manipulation with the fingers.

6.3 MEASURES TO MINIMIZE BIAS: RANDOMIZATION AND BLINDING

The Biostatistics Unit will develop a randomization procedure using a permuted block design within the Biostatistics Randomization Management System (BRMS) system. Additional details of the procedure, including required record keeping, will be further developed upon approval of this protocol. The Biostatistics Unit has extensive experience in implementing and in producing detailed documentation for such procedures. The patient will be blinded to their randomization group.

6.4 STUDY INTERVENTION COMPLIANCE

The surgeon and the operating room staff will be notified of the treatment arm prior to the start of the surgery. All patient outcome measurements are part of the standard of care for a total knee arthroplasty patient.

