2 INTRODUCTION

2.1 STUDY RATIONALE

Total joint arthroplasty can result in significant blood loss. Bone wax is a well-known topical hemostatic agent comprised of a mixture of beeswax, paraffin, and isopropyl palmitate. This inexpensive agent works by sealing the bleeding site and tamponades bleeding from the exposed cancellous bone.²

The purpose of this study is to assess whether the application of bone wax to the exposed cancellous bone, after the cemented implants are in place, will provide superior hemostasis in a total knee arthroplasty patients compared to patients who do not have the bone wax applied. Hemostasis will be assessed by calculating blood loss using the Hb-balance formula.

This will be a prospective, randomized, single-blinded, superiority study in patients scheduled for a primary unilateral TKA with [name] or [name]. The restriction of this study to two surgeons will limit variations in the outcomes being measured due to differences in surgical technique. The application of bone wax to the exposed cancellous bone has been the standard of care for four years by Drs. [name] and [name]. The surgeons technique is to apply the bone wax to the exposed cancellous bone after the implant has been cemented in place thereby eliminating the risk for any issues with bone ingrowth.

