Another method used intraoperatively to maintain hemostasis is the application of a pneumatic tourniquet. During TKA, a pneumatic tourniquet is applied to the upper part of the thigh on the operative limb and inflated to a pressure determined by the surgeon. The tourniquet applies pressure to the limb to occlude the blood supply. The tourniquet is released by the surgeon at the end of the case and electrocautery is then used to seal any bleeding vessels.

Significant blood loss intraoperatively and post-operatively can produce complications. The use of hemostatic agents such as bone wax may further facilitate hemostasis during a total knee arthroplasty. Bone wax was developed in 1885 by a British neurosurgeon named Sir Victor

Horsley. Bone wax consists of beeswax, paraffin and isopropyl palmitate. Since its first documentation of hemostatic potential in 1892, there has been a number of modifications to its formulation.² The main component that remains is beeswax. Today bone wax is used in a variety of surgical procedures as a mechanical hemostatic agent. During total joint arthroplasties bone wax is softened and applied firmly on the cancellous bone around the prostheses.

Bone wax increases hemostasis because of its ability to immediately seal and plug marrow sinusoid and consequently prevent oozing of blood.³ Studies have shown other benefits of bone wax, like the ability to decrease post-operative edema and pain.⁵ In the study conducted by Moo et al. 100 patients were recruited into a 1:1 randomization: (1) bone wax (2) control. Measurements were taken for height, weight, serum hemoglobin levels and base line lower limb diameters. Hemoglobin (Hgb) and Hematocrit (Hct) levels were checked on POD 1 and POD 3. Each study subject underwent total knee arthroplasty using standard procedures. Bone wax was applied around the prosthesis to obtain hemostasis in these areas. A significant decrease in blood loss was observed in the bone wax group at POD 1 and 3. None of the patients in the bone wax cohort required blood transfusions. Three patients in the control group required a blood transfusion.²

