2.3 RISK/BENEFIT ASSESSMENT

2.3.1 KNOWN POTENTIAL RISKS

The surgical techniques used to promote hemostasis will be consistent for all patients, except for the use of bone wax applied to the exposed cancellous bone following insertion of the prosthesis. There is a potential that patients in the control arm could have increase bleeding. The following risks have been shown to be associated with the use of bone wax: failed bone healing, foreign body reaction, granuloma growth, thrombosis, infection, and nerve compression

There is a small risk of an unintended breach of confidentiality, as there is in any research study that collects subjects' health information.

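### The surgeon and operating room staff are told the arm before surgery, although it is not needed until the implants are cemented; the result could be withheld until then at little cost

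*Combined protocol and SAP*

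**What the plan says.** On disclosure, section 6.4 reads: "The surgeon and the operating room staff will be notified of the treatment arm prior to the start of the surgery". Section 4.2 agrees for the operating room staff: eligibility is verified on the operative day, the patient is randomised and the staff are told. It gives no later point of release.

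On when the arm is first acted on, section 2.1 reads: "The surgeons technique is to apply the bone wax to the exposed cancellous bone after the implant has been cemented in place". Section 6.1.1 has the wax "applied firmly on the exposed cancellous bone around the prostheses by the orthopaedic surgeon after implant cementing".

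On what comes before that, section 6.1.2 has the surgeons measure exposed bone. The measurements start "Once the distal femoral cut and prep for the chamfer cuts and notch cut is complete". Section 2.2 describes a thigh tourniquet "inflated to a pressure determined by the surgeon".

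On what comes after, section 2.2 reads: "The tourniquet is released by the surgeon at the end of the case and electrocautery is then used to seal any bleeding vessels".

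On the premise of the comparison, section 2.3.1 reads: "The surgical techniques used to promote hemostasis will be consistent for all patients, except for the use of bone wax". Section 4.2 makes the same commitment for the other blood-sparing measures. Section 2.1 adds that waxing exposed bone "has been the standard of care for four years" for the two operating surgeons.

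On blinding, the title and section 4.1 call the trial single-blinded. Section 4.2 blinds the patient and the postoperative hospital staff. No section claims that the surgeon is blinded.

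**The concern.** The comparison rests on everything except the wax being done alike in both arms. The surgeon cannot be blinded once wax is applied or left out, but nothing before that moment depends on the arm. Under section 6.4 the whole earlier part of the operation is nevertheless carried out with the arm known, by surgeons for whom wax is routine.

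Three things are exposed to that knowledge without need:

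- **Conduct of the operation up to cementing.** This includes the bone cuts.
- **The exposed-bone record.** Section 2.2 faults an earlier retrospective study for not assessing uncovered bone during surgery, says that the residual cut area may be related to blood loss, and offers the surgeons' measurement as an improvement. Readers may use it to judge whether the arms were comparable, so it is worth more if taken without knowledge of the arm.
- **Exclusions during the case.** Section 4.2 excludes patients who cannot be treated under the department guidelines and does not say whether this can happen after randomisation. If it can, a decision made before cementing would be made with the arm known.

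**Working it through.** The check is mainly one of sequence. Each step is set against whether it needs the arm, and who would know it.

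| Step | Source | Arm needed? | Surgeon knows arm now | After the fix |
|---|---|---|---|---|
| Tourniquet inflation | 2.2 | No | Yes | No |
| Bone cuts | 6.1.2 | No | Yes | No |
| Exposed-bone measurement | 6.1.2, 1.3 | No | Yes | No |
| Cementing | 2.1, 6.1.1 | No | Yes | No |
| Wax or no wax | 2.1, 6.1.1 | Yes | Yes | Yes |
| Tourniquet release, cautery | 2.2 | No | Yes | Yes |
| Surgeon's objective KSS at 8 weeks | 9.1 | No | Yes | Yes |

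Four steps come before the arm is needed, and later disclosure would protect all four. The last two rows stay unblinded under either plan.

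**Is early notice needed for preparation?** Nothing suggests so. Section 6.1.2 has the wax used straight from the package, and section 6.2.4 has it softened in the fingers.

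**Is the order already fixed elsewhere?** No. The schema (1.2) and schedule (1.3) put randomisation on the day of surgery, and the schedule puts exposed-bone grading there too. Neither places disclosure relative to grading or cementing. Section 6.3 leaves the details of the randomisation procedure to be developed.

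**Should randomisation or only disclosure be delayed?** Sections 7.2 and 9.3 define the ITT population as all randomised patients. If randomisation itself moved to after cementing, a case that departed from plan before then would never enter the ITT set. If only disclosure moves, that case is in the set, as it is today. Delaying disclosure alone therefore leaves the analysis population unchanged.

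**Does the planned power change?** No. Section 9.2 gives SDs of 282.7 and 259.8 mL, and √[(282.7² + 259.8²)/2] = 271.5 mL, as stated. With 50 per arm, SE = 271.5 × √(2/50) = 54.3 mL. For 153 mL the noncentrality is 153/54.3 = 2.82. A two-sided t-test at 0.05 with 98 df then has 79.7% power, against the stated 80%. Section 9.2 does not state sidedness; two-sided reproduces its figure. None of these inputs depends on when the surgeon is told.

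**Can the bias be sized?** No. That would need the shift in blood loss caused by knowing the arm and the share of it arising before cementing. The documents give neither, so no error rate is offered.

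**The case against.** The strongest reply is that nothing here is broken. The trial says that it is single-blinded, and telling a surgeon the arm beforehand is conventional when the surgeon must deliver it. A reader might infer that early notice contradicts the blinding claims. It does not, because those claims cover only the patient and postoperative staff. That part of the objection stands.

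Second, the sentence sits under the compliance heading, which suggests a purpose: making sure that the assigned arm is delivered. Control cases require the surgeons to omit a habitual step, and news that arrives just when wax would normally go on could lead to wax in a control. Under ITT that would dilute the effect. This is a real downside and should be managed, but notice given just before the wax step serves compliance as well as notice before the case.

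Third, the route to the primary endpoint is thin. The tourniquet occludes flow, and the surgeon-controlled hemostasis described comes at its release. Blood loss is calculated from routine hemoglobin values drawn while blinded staff give the care. The remark about tourniquet pressure is general background, and nothing suggests that pressure would vary by arm. This stands, and it limits the size of the gain.

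Fourth, exposed bone is computed by a fixed formula from linear measurements and implant size, and it enters no planned analysis (9.4.2, 9.4.3, 9.4.7, 9.4.9). This also stands. The gain is in how far readers can trust a descriptive record.

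Fifth, opening an assignment during the case puts the patient's blinding at some risk, since the patient may be awake under spinal anesthesia. The answer is to show the arm in writing and not speak it.

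**Conclusion.** The point holds as an optional, low-cost improvement. The arm is disclosed earlier than the intervention requires. Withholding it until after cementing would keep the cuts, the exposed-bone record and any exclusion decided before cementing free of that knowledge. This rests on the sequence in sections 2.1, 6.1.1 and 6.1.2 being followed in practice, and on staff being available to hold and open the assignment.

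The size of the benefit is unknown and may be small. A reader might go further and infer that the primary result will be biased or its error rate inflated. The documents do not support that: they contain no evidence that conduct would differ by arm and no figure from which to size a shift. A reader might also infer that later release would blind the surgeon. It would not, because everything from the wax step onward, including the surgeon's objective KSS measurements, remains open to the surgeon.

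**What to change.** Keep randomisation in BRMS on the day of surgery before the case, and delay only disclosure. In sections 4.2 and 6.4, replace the notification sentences with wording such as:

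> The patient is randomised in BRMS on the day of surgery before the case. The result is withheld from the surgeon and the operating team, for example as a sealed print-out held by existing staff, until exposed bone has been recorded and the implants are cemented. It is then shown to the team in writing and is not read aloud. The time of release is recorded.

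Show the same order in sections 1.2 and 1.3: randomisation, exposed-bone record, cementing, release of the arm, wax or no wax. Put the holding and release step in the procedure that section 6.3 still has to develop. A print-out of the BRMS assignment needs no separate back-up allocation list. Report as limitations that hemostasis after cementing and the surgeon's objective KSS measurements remain unblinded to the surgeon.

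The cost is a few sentences and one added step per case. The downsides to plan for are:

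- someone must hold and open the assignment during the case;
- wax must be on hand for every patient;
- the patient may be awake, so the arm must stay unspoken;
- the team must be ready to leave out a habitual step in controls.

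If the investigators prefer early notice, a sentence in section 6.4 saying why would be enough.
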